***Outcome Measures:***

***Rest pain:*** Rest pain will be measured bilaterally with a 10-cm visual analog scale (VAS) at baseline and each follow-up visit. Patients will be instructed to place a mark on a line from 0 cm (no pain) to 10 cm (worst pain previously experienced) that would best describe the level of pain in the index limb during the previous 24 hours prior to examination. The distance from the 0-cm mark will then be measured and recorded.

***Cardiopulmonary Treadmill Exercise Test:*** Participants will perform a graded, symptom-limited exercise test on a treadmill following the Gardner protocol (treadmill speed of 2 mph, 0% grade with increments of 2% every 2 min), as described previously by our group (5). During the test, the microvascular oxygenation status of the gastrocnemius muscle of the leg undergoing revascularization will be continuously monitored using a near-infrared spectrometer (NIRS) (5). Gas exchange and ventilatory variables will be measured breath-by-breath during exercise and recovery using a computer-based system (5).

***Leg hemodynamics:*** The ankle-brachial index (ABI) and the toe-brachial index (TBI) will be measured bilaterally following standard of care practices. Transcutaneous PO2 (TcPO2) will be measured only in the leg undergoing revascularization.

***Quality of life assessment:*** Participants will be asked to fill out the the 36-item Short-Form Health Survey and the Vascular quality of life questionnaire (VascuQoL-6) health-related quality of life questionnaires.

***Biomarkers of coagulation and fibrinolysis:*** Blood levels of markers of coagulation and fibrinolysis will be measured in the Pathology laboratory using standard methods.

**Potential risks to subjects:**

***Treadmill Cardiopulmonary Exercise Test:*** Intervention trials in PAD have demonstrated the ability of the graded treadmill exercise test to safely and robustly quantify changes associated with efficacious interventions (3). This test has been shown to be very safe, even in populations with underlying high-risk cardiovascular diagnosis (8), including patients with PAD (1). However, there is a chance that patients may experience chest pain, intolerable dyspnea, leg cramps, staggering, diaphoresis, and dizziness. The Treadmill Test will be conducted in the Heart Station where a Cardiologist is present 8AM to 5PM daily. Participants with an abnormal baseline treadmill stress test, including signs of coronary ischemia and an exaggerated pressor response, will be excluded from the study.

***IPC:*** There are no known side effects to IPC. It has been reported that patients with severe PAD may experience pain during initial exposure to the treatment.

**Venous blood sampling:** During blood sampling there is a risk of pain from the needle. Bleeding, local swelling, bruising and formation of a hematoma might also occur around puncture site.

**Measurement of calf muscle oxygenation:** There are no risks associated with calf muscle oxygenation measurements.

**Rest pain measurement:** There are no risks associated with rest pain measurements.

## **6.0 Reporting of Adverse Events or Unanticipated Problems involving Risk to Participants or Others**

If the patient is injured due to participation in this study, he/she will be instructed to contact the study investigators. Patients will also be advised to contact the Human Subject Office at Indiana University if they have questions about their rights while taking part in the study.

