#### **Exclusion criteria**

- 1) Chronic kidney disease (eGFR <30 by MDRD or Mayo or Cockcroft-Gault formula)
- 2) Open and/or non-healing wounds in the areas covered by the IPC cuff
- 3) Inability to walk on the treadmill
- 4) Abnormal baseline treadmill stress test
- 5) Walking limited by a symptom other than PAD
- 6) Inability to independently and correctly position the IPC cuff on legs and feet
- 7) Presence of any clinical condition that makes the patient unsuitable to participate in the trial
- 8) Concern for inability of the patient to comply with study procedures and/or follow up (e.g., alcohol or drug abuse)
- 9) Acute deep vein thrombosis (DVT) either suspected or diagnosed
- 10) Uncontrolled infection
- 11) Increased pain with ArtAssist device operating or with worsening skin tissue condition
- 12) During episodes of inflammatory phlebitis or pulmonary embolism
- 13) When increased venous or lymphatic return is undesirable including presumptive evidence of congestive heart failure

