At least 72 hrs after visit 1, subjects will be asked to return for visit 2. Participants will be asked to lay supine and a member of the Vascular Access Team (VAT) will draw a blood sample (20 mL) from one antecubital vein in the arm. Next, participants will undergo the bilateral assessment of the ankle-brachial index (ABI), the toe-brachial index (TBI) and transcutaneous PO2 (TcPO2) following standard of care practices. Patients will be asked to report the pain in their legs using visual analog scale (VAS). Patients will then be escorted to the exercise testing lab to undergo a graded, symptom-limited cardiopulmonary exercise test on a treadmill as described for visit 1. At the end of the session, subjects will be asked to fill out two questionnaires to assess generic (36-item Short-Form Health Survey) and disease-specific (Walking Impairment Questionnaire) quality of life. Next, patients will be trained on how to operate the IPC pump on how to wear the cuffs and will undergo a 15-min practice treatment session. At the end of the practice session, participants will be trained on: 1) how to wash and care for the inflatable cuffs, 2) how to turn the pump on and off, 3) how to record usage time on a logbook. Participants will receive the ArtAssist device (ACI Medical Inc, San Marcos, CA, USA) for IPC application. This device applies compressions to both the calf and foot, at a pressure of 120 mmHg for 3 seconds

per cycle, and this continues for three cycles per minute with a 1-second delay between different segment inflation. Patients allocated to the control group will receive a sham device, that applies a pressure of 30 mmHg at the frequency specified above. Participants on both groups will be asked to apply the cuffs to both legs and use the device while seated for 2 hours daily for 3 months. This session (Visit 2) will be performed at IU's Methodist Hospital and is expected to last approximately 4 hours.

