Patients in both groups will receive weekly telephone calls from the study coordinator to verify compliance and will receive a logbook to record their sessions. A timer built into the IPC unit, and inaccessible to patients, will also provide an estimate of the patients' compliance with the treatment regimen. The logbook is intended to assist the participant keep track of the daily treatments; it will not be a protocol deviation if the logbook is not returned at the end of the treatments. Compliance with daily treatment will be formally assessed and documented with the weekly phone call from the study team. A protocol deviation will occur when either 3 consecutive home treatments are not performed or when 8 or more home treatments are not performed during the 3-month treatment period.

Outcomes will be reassessed after 1 month of treatment (end of week  $4 \pm 7$  days) and at the completion of the intervention (end of week  $12 \pm 7$  days). The protocol for these outcome visits will be similar to visit 2 as detailed in the table below. To ensure that the chronic rather than the acute effects of IPC are investigated, participants will be asked to interrupt the treatment 48 hrs prior to the outcome sessions. Although interrupting the treatment 48 hours prior to the outcomes sessions is desired for testing consistency it will not be a protocol deviation if a subject does not interrupt the treatment as instructed.

Visit #	Time point	Procedures
1	Baseline	Consenting Rest pain measurement Demonstration of device operation and proper cuff placement Familiarization with Cardiopulmonary Treadmill test
2	Baseline	Blood draw ABI, TBI and TCPO 2 Rest pain measurement Cardiopulmonary Treadmill test Quality of life questionnaires Familiarization with treatment
3	1 month	Blood draw ABI, TBI and TCPO 2 Rest pain measurement Cardiopulmonary Treadmill test Quality of life questionnaires
4	3 months	Blood draw ABI, TBI and TCPO 2 Rest pain measurement Cardiopulmonary Treadmill test Quality of life questionnaires

**Table 1:** Study timeline and experimental procedures that will be performed on each session

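### The protocol describes no active adverse-event question at any call or visit, so events during home use are likely to be under-counted in both arms

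*Combined protocol and SAP*

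**What the plan says.** Section 6.0 has two sentences. The first is "If the patient is injured due to participation in this study, he/she will be instructed to contact the study investigators"; the second concerns questions about patients' rights. The section does not define an adverse event, and it sets no question for staff to ask, no investigator assessment of cause, no recording rule and no reporting timeline.

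Section 5.0 provides regular contact, but for another purpose: "Patients in both groups will receive weekly telephone calls from the study coordinator to verify compliance". What the calls produce is also stated: "Compliance with daily treatment will be formally assessed and documented with the weekly phone call from the study team". Table 1 lists blood draw, hemodynamics, rest pain, treadmill test and questionnaires at visits 3 and 4, with no adverse-event or skin check. Section 8.0 names no safety or tolerability summary.

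On what might be expected from the device, the risk paragraphs in section 5.0 state "There are no known side effects to IPC" and continue directly with "It has been reported that patients with severe PAD may experience pain during initial exposure to the treatment". Exclusion criterion 11 in section 3.0 reads "Increased pain with ArtAssist device operating or with worsening skin tissue condition". The active pump works "at a pressure of 120 mmHg for 3 seconds" per cycle. For the other arm, "Patients allocated to the control group will receive a sham device, that applies a pressure of 30 mmHg". Both arms use the device at home for 2 hours a day over 3 months.

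**The concern.** The described route has three filters: the patient must notice a problem, regard it as an injury caused by the study, and make contact. Soreness during compression or a skin change under the cuff can fail at any of them. The protocol itself recognises pain with the device and worsening skin as relevant, yet it sets no way to detect either during home use.

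Section 8.0 says the pilot should show that the intervention can be implemented and should support a larger randomized trial. Whether patients tolerate the pump bears directly on that. A pilot run as written could report no events because nobody was asked, and that statement could be carried into the next protocol. An event between visits could also go unnoticed by the study team.

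**Working it through.** **1. Does any other part of the plan fill the gap?**

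| Contact or measure | What it could reveal | What the plan requires to be recorded |
|---|---|---|
| Weekly calls, both arms (5.0) | Anything the patient is asked | Compliance with daily treatment |
| Built-in timer and missed-session rule (5.0) | Non-use: 3 consecutive, or 8 or more in total, is a protocol deviation | The deviation; no reason |
| 15-minute practice session, visit 2 (5.0) | Pain on first exposure | Nothing on tolerability |
| Rest-pain VAS at each visit (5.0, Outcome Measures) | Leg pain over the previous 24 hours | The score |
| Visits 3 and 4 (Table 1) | Anything the patient is asked | No adverse-event or skin item |

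The VAS does not substitute for a question about the device. Patients are asked to stop treatment 48 hours before outcome visits, and the scale looks back 24 hours. In a patient who follows the instruction, the recall window contains no compression. At visit 2 the VAS comes before the practice session in the described order.

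**2. Illustration of size.** The only design figure is 4 patients per arm (4.0 and 8.0). The documents give no event rate, so there is no planned safety figure to reproduce. Let p be the probability that a patient has an event and c the probability that the event reaches the investigators. **Both are assumptions.** With patients independent,

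P(at least one event recorded among 4) = 1 − (1 − p·c)^4.

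| p | c = 1 | c = 0.5 | c = 0.25 |
|---|---|---|---|
| 0.10 | 1 − 0.900^4 = 34.4% | 1 − 0.950^4 = 18.5% | 1 − 0.975^4 = 9.6% |
| 0.25 | 1 − 0.750^4 = 68.4% | 1 − 0.875^4 = 41.4% | 1 − 0.9375^4 = 22.8% |
| 0.50 | 1 − 0.500^4 = 93.8% | 1 − 0.750^4 = 68.4% | 1 − 0.875^4 = 41.4% |

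The range is thus 34% to 94% with full capture, and 10% to 68% when a quarter to a half of events are volunteered.

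**3. What full capture would still leave open.** If 0 of 4 patients have an event, the one-sided 95% upper bound solves (1 − p)^4 = 0.05, so p = 1 − 0.05^(1/4) = 0.527, or 53%.

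**4. Contacts already planned.** 12 weekly calls × 8 patients = 96 calls. At 1 to 2 minutes each (an assumption), added questions would take 96 to 192 minutes over the whole trial.

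**The case against.** The strongest reply is that the plan is not blind to intolerance. The pain it names is pain on first exposure, and the practice session puts 15 minutes of use inside a study visit. A patient who cannot tolerate the pump would probably use it less, and the calls and the timer check use. This stands in part: severe intolerance would tend to show as missed sessions. But the reason need not be recorded, so pain, inconvenience and forgetting look alike. A patient who keeps using the pump despite pain or skin change would not show up this way at all.

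Some stronger readings are tempting but not supported:

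- A reader might infer that events can be captured only if a patient calls in, and that they will certainly be missed. The protocol is silent about asking; it does not stop staff from noting what they hear. Section 6.0 gives the only route described, and under-counting is the likely direction, not a demonstrated result.
- A reader might infer that the protocol presents deep vein thrombosis, phlebitis, pulmonary embolism and heart failure as harms of the device. In section 3.0 they are conditions that exclude a patient. Only first-exposure pain and criterion 11 bear on tolerability.
- A reader might infer that the problem concerns the 120 mmHg arm alone. The same rule covers the sham arm, and the documents do not show that reporting would differ by arm.
- A reader might infer that tolerability, or implementation of the intervention, is the pilot's leading purpose. Section 8.0 lists implementation third, after recruitment and randomization. Section 2.0 states an efficacy-oriented objective, and tolerability is not a stated outcome.

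It is also fair to say that four patients per arm cannot establish tolerability however events are collected.

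**Conclusion.** The point holds in limited form. The protocol describes only patient-initiated reporting of injuries the patient attributes to participation, and no written item at the calls, at the visits or in the analysis makes up for it. Followed as written, this is likely to under-count device-related pain, skin change and other events during home use, in both arms.

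The amount cannot be determined from the documents. The percentages rest on assumed risks and reporting shares and show scale only. Given the 53% bound, the gain from asking is better detection and an interpretable record, not proof that the device is tolerated. The conclusion also rests on the protocol text alone; any instructions in consent material are outside it and are not counted as a gap. The change is worth making before enrolment because it is cheap and needs no new contact.

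**What to change.** 1. At each weekly call and at visits 3 and 4, ask both arms the same short list, worded identically: pain with the device, skin change and an open question about any other event.
2. Record every event whatever its presumed cause, so that the patient does not have to judge causality. State this in section 6.0 and add the item to Table 1.
3. Record the reason for missed sessions, and note tolerability at the practice session.
4. Add to section 8.0 a descriptive tabulation of events and of reasons for missed sessions by arm.
5. Reconcile "There are no known side effects to IPC" with the sentence after it and with exclusion criterion 11. Which statement is right, and how any event is managed, is for the investigators.

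**Cost:** one to two minutes on calls already planned and one form, with no new visits. The tabulation should be presented as descriptive, since 4 patients per arm cannot support a comparison of event rates.

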## **7.0 Study Withdrawal/Discontinuation**

Participation in this study is voluntary. Participants may choose not to participate or, if they agree to participate, they can withdraw their participation at any time without penalty or loss of benefits to which they are otherwise entitled.

## **8.0 Statistical Considerations**

The results obtained in this pilot experiment will allow us to demonstrate the feasibility of recruitment, randomization and intervention implementation and will provide the necessary data to support pursuit of a larger randomized clinical trial. Walking tolerance, limb hemodynamics and muscle oxygenation parameters will be compared between groups with two-way repeated-measures ANOVA, followed by Tukey's post hoc test when appropriate. We estimate that 4 subjects per group are needed to show feasibility and to provide support to our hypothesis that repeated exposure to IPC improves leg hemodynamics and reduces leg pain in patients with severe PAD recovering from peripheral revascularization.

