## 2.0 Rationale and Specific Aims

One emerging adjunctive therapy that has the potential to enhance the benefits of revascularization procedures for severe PAD is the application of intermittent pneumatic leg compressions (IPC). This is a non-invasive intervention, consisting of an air pump inside inflatable cuffs that are wrapped around the feet, ankles, and calves and worn for two hours daily. Every 20 second, the cuffs rapidly inflate, followed by rapid deflation. We and others have previously shown that exposure to IPC markedly enhances leg blood flow and vascular shear-stress in the arteries of the leg (2, 6, 7). Our preliminary work shows that 2 weeks of daily application of IPC enhances exercise tolerance in a model of PAD, in part by enhancing blood flow to collateral-dependent tissues (4). IPC has also been shown to reduce amputation rates in patients with CLI without a revascularization option. The objective of this *pilot* study is to establish evidence to support the validity of IPC in improving the outcome of lower-extremity revascularization for severe PAD. Our central hypothesis is that the treatment with IPC will lead to greater improvements in leg hemodynamics as compared to a sham device. As a result, we anticipate that patients treated with IPC will report less rest pain, have enhanced walking endurance and improved calf muscle oxygenation resulting in a subsequent improvement in quality of life. To test this hypothesis, we propose the following specific aim:

***SPECIFIC AIM:*** Determine the effects of IPC following revascularization in patients diagnosed with severe PAD.

Figure 1: Intermittent pneumatic compression device

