Patients will be enrolled in the study approximately 3 months after the revascularization procedure and will be randomly assigned to one of two groups: IPC or placebo pump. Patients will receive a commercially available IPC device (ArtAssist, ACI Medical, San Marcos, CA) and will be asked to apply the treatment to both legs at home for 2 hours daily during 3 consecutive months. Prior to the onset of the treatment and 1 and 3 months after daily home-based IPC, we will assess patient's leg hemodynamics, rest pain, calf muscle oxygenation during exercise, walking endurance and quality of life. We expect beneficial changes in leg hemodynamics, reduced rest pain, increased levels of exercise tolerance, improved calf muscle oxygenation during exercise, and improved quality of life, (QOL) as assessed by responses to VascuQol and SF36 questionnaires. The ankle-brachial index (ABI), the toe-brachial index (TBI), and rest pain will be assessed on the leg undergoing the revascularization procedure and the opposite leg. Transcutaneous PO2 (TcPO2) and calf muscle oxygenation will only be assessed in the leg undergoing revascularization.

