## **4.0 Enrollment/Randomization**

Patients will be recruited by [name] and his associates at the Indiana University Health Methodist Hospital, Indiana University Health West Hospital and Indiana University Health Arnett. Patients that fulfill the inclusion criteria and are interested in participating in the protocol will receive detailed instructions about the experimental set-up and measurements and will be given a consent form. After providing consent, patients will be asked to complete the baseline assessment, including the assessment of leg hemodynamics, rest pain, calf muscle oxygenation during exercise, walking endurance and quality of life. Patients will be randomized into one of two groups: IPC (n=4) or placebo pump (n=4). Patients will receive an IPC device and will be asked to apply the treatment at home for 2 hours daily during 3 consecutive months. Outcomes will be reassessed 1 and 3 months after the onset of home-based treatment.

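### Section 8.0 plans an unadjusted two-way repeated-measures ANOVA and names no treatment contrast; with 4 v 4 patients it should use the baseline already collected through a common baseline mean

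*Combined protocol and SAP*

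**What the plan says.** The whole analysis plan for these outcomes is one sentence in Section 8.0: "Walking tolerance, limb hemodynamics and muscle oxygenation parameters will be compared between groups with two-way repeated-measures ANOVA", with Tukey's test to follow where called for. It does not name the two factors, the levels of time, the term that tests the pump, or any covariate.

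The outcomes have a pre-treatment value. Section 2.0 places assessments "Prior to the onset of the treatment and 1 and 3 months after daily home-based IPC". Section 4.0 describes the baseline work ahead of allocation: "After providing consent, patients will be asked to complete the baseline assessment, including the assessment of leg hemodynamics, rest pain". Its next sentence is "Patients will be randomized into one of two groups: IPC (n=4) or placebo pump (n=4"). In Section 5.0 the device is handed over only after the second baseline session's testing.

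The hypothesis in Section 2.0 concerns improvement: "treatment with IPC will lead to greater improvements in leg hemodynamics as compared to a sham device". On size, Section 8.0 says "We estimate that 4 subjects per group are needed to show feasibility and to provide support to our hypothesis", without an alpha, power, SD, effect size or between-visit correlation.

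**The concern.** A hypothesis about improvement needs the baseline value, yet Section 8.0 does not say how baseline enters. The natural reading is group by time over three visits. With only the two follow-up visits, neither factor would have more than two levels, and Tukey's test would have work only among the interaction cells.

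On that reading, the term that literally compares the groups averages in a visit at which nobody has been treated. The other candidate, the group-by-time term, works on unadjusted change. It subtracts the whole of any chance baseline difference, when only a fraction rho of it is expected to persist. It also estimates a baseline group difference that randomisation makes zero in expectation.

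If baseline is instead left out of the model, the follow-up difference is still unadjusted and carries rho times the imbalance. No usual reading of the sentence adjusts for baseline.

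At stake is the estimate that this pilot passes on to the planned larger trial. With four patients per arm, a sizeable starting difference is likely.

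**Working it through.** **Inputs from the protocol.** n = 4 per arm (Sections 4.0 and 8.0); visits at baseline, 1 month and 3 months (Sections 2.0, 4.0 and 5.0). The 4 per group has no derivation to reproduce.

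**Assumptions, because the documents give no figures.** Outcome SD 1 at each visit, equal correlation rho between visits (compound symmetry), two-sided 5%, no dropout. Let d0, d1 and d3 be the IPC-minus-sham differences in means at the three visits.

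**1. Chance imbalance.** SD(d0) = sqrt(2/4) = 0.71. P(|d0| > 0.5) = P(|Z| > 0.5/0.71) = 48%. P(|d0| > 1) = P(|Z| > 1/0.71) = 16%.

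**2. Group main effect with baseline as a level.** Its estimate is (d0 + d1 + d3)/3. With true effects e1 and e3, its expectation is (0 + e1 + e3)/3, which is two thirds of the follow-up average (e1 + e3)/2. A steady effect of 1.0 SD is therefore estimated as 0.67. Each 1 SD of baseline imbalance moves it by (1 + 2 rho)/3, which is 0.67 at rho 0.5.

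**3. The 3-month change contrast, d3 - d0.** It is not diluted. Given d0, its expected shift is rho d0 - d0 = -(1 - rho) d0. Its variance is (2/4) x 2(1 - rho) = 1 - rho.

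**4. Common baseline mean, d3 - rho d0.** With rho known, the variance is (2/4)(1 - rho²), so its ratio to the change contrast is (1 + rho)/2. Estimating rho from 8 patients costs part of that gain; the simulated ratio includes this cost.

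**5. Ordinary ANCOVA at 3 months.** Estimating a free slope from 8 patients multiplies the variance by about 1 + 1/4 = 1.25, giving 1.25 x (2/4)(1 - rho²).

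| rho | Shift of change contrast per 1 SD imbalance | Var, change | Var, ANCOVA | Common baseline / change, rho known | Same ratio, rho estimated |
|---|---|---|---|---|---|
| 0.3 | -0.70 | 0.70 | 0.57 | 0.65 | 0.69 |
| 0.5 | -0.50 | 0.50 | 0.47 | 0.75 | 0.80 |
| 0.7 | -0.30 | 0.30 | 0.32 | 0.85 | 0.92 |
| 0.85 | -0.15 | 0.15 | 0.17 | 0.925 | 0.99 |
| 0.9 | -0.10 | 0.10 | 0.12 | 0.95 | about 1.0 |

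With rho estimated, the common-baseline estimate moves by only about 0.02 to 0.06 SD per 1 SD of imbalance.

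**6. Power by simulation.** Effects of 1 SD at 1 month and 2 SD at 3 months; critical values for the last two columns set to 5% at each rho:

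| rho | Group term | Group-by-time (2 df) | 3-month change | Common baseline |
|---|---|---|---|---|
| 0.3 | 37% | 46% | 60% | 77% |
| 0.5 | 31% | 60% | 73% | 83% |
| 0.7 | 27% | 83% | 92% | 95% |
| 0.85 | 24% | 99% | 99.7% | 99.8% |

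Under the null, the group, group-by-time and change tests each reject in about 5% of trials with mean estimates near 0. The common-baseline test, referred to t with 8 df and not calibrated to a known rho, rejects in about 4 to 5%.

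**The case against.** The strongest reply is that this is under-specification in a feasibility pilot. A reader might infer that Section 8.0 states that baseline is an outcome level, that the comparison is therefore biased, and that precision is lost in general. The documents support none of these as stated.

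- **Baseline as a level is an inference.** The sentence would also fit an ANOVA of changes or of the follow-up visits alone.
- **The diluted term may not be the one intended.** A hypothesis of greater improvement points to the group-by-time term, which is not diluted. No text makes the group main effect the treatment test.
- **Bias is the wrong word for chance imbalance.** Averaged over randomisation, the change comparison is unbiased. The error is conditional on the imbalance that occurs, and the standard error already allows for it.
- **The precision gain is conditional.** It needs rho of about 0.7 or lower, and rho may be higher for repeated vascular or treadmill measures. It also needs the right model. Ordinary ANCOVA is worse than the change contrast at rho 0.7 and above. A simulated unstructured fit was too (variance 0.32 v 0.30 at rho 0.7, 0.17 v 0.15 at 0.85), with 9 to 10% null rejection on 5 to 6 df without further correction.
- **The consequence is limited.** No primary endpoint, alpha or powered test depends on this choice, and data collection is the same either way.

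All of this stands as a limit on the point. It does not remove the omission: no section adjusts for baseline or names the contrast, and Section 8.0 wants the results to support the efficacy hypothesis and a larger trial.

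**Conclusion.** The point holds in a limited form. Section 8.0 names an unadjusted ANOVA and no treatment term, and a better use of data already collected is available.

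The only systematic distortion is dilution to two thirds, and it arises only if baseline is a time level and the group main effect is read. Otherwise the cost is an estimate that follows chance imbalance, by 0.5 SD per 1 SD of imbalance at rho 0.5, plus avoidable variance. Relative to the 3-month change contrast, the common-baseline estimate has about 30%, 20% and 8% less variance at rho 0.3, 0.5 and 0.7, and about the same at 0.85 to 0.9.

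The variance and power figures rest on assumed SD 1, compound symmetry and complete data; the power figures also assume large effects. The imbalance probabilities need only n = 4 per arm and approximate normality.

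**What to change.** Replace the comparison sentence in Section 8.0 so that it states:

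- The treatment contrast is the IPC-minus-sham difference at 3 months, and also at 1 month.
- It is estimated in a repeated-measures model with baseline, 1-month and 3-month visits, one baseline mean common to both groups, and a separate group difference at each follow-up visit.
- The covariance is compound symmetry, as the ANOVA already assumes. With 8 patients, neither an unstructured covariance nor ordinary ANCOVA is used.
- Each estimate is reported with a 95% CI using a small-sample df correction, and the group main effect is not interpreted.

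The common mean relies on baseline being taken before allocation, as the order of Section 4.0 indicates; the revised text should confirm this.

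The cost is a few lines of text and a mixed-model routine in place of a standard ANOVA procedure, with no new patients, visits or measurements. The downsides are reliance on compound symmetry, which 8 patients can barely check, and a negligible gain if rho is high.

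### As usually run, the planned repeated-measures ANOVA can discard observed 3-month values, and its time tests rest on an unaddressed sphericity assumption; 4 v 4 patients can ill afford the loss

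*Combined protocol and SAP*

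**What the plan says.** The analysis plan is one sentence in Section 8.0. It names three outcome families (walking tolerance, limb hemodynamics, muscle oxygenation), which "will be compared between groups with two-way repeated-measures ANOVA, followed by Tukey's post hoc test when appropriate". No rule for a missing visit, sphericity check or correction, covariance structure, software or alpha is given.

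The data come from three time points. Baseline is taken before treatment, and Section 4.0 adds: "Outcomes will be reassessed 1 and 3 months after the onset of home-based treatment". Section 5.0 allows 7 days either side of weeks 4 and 12. Section 4.0 allocates 4 patients to each group. Section 7.0 tells participants that "they can withdraw their participation at any time without penalty". On size, Section 8.0 says: "We estimate that 4 subjects per group are needed to show feasibility", and presents the results as support for a larger trial.

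**The concern.** Two features of the named method matter here.

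First, a conventional two-way repeated-measures ANOVA needs a value at every visit. A patient with good baseline and 3-month values who misses the 1-month visit, or has one failed TcPO2 or NIRS recording at it, drops out of that outcome altogether. One patient is an eighth of the trial and a quarter of an arm.

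Second, the time and group-by-time F tests assume sphericity: the differences between each pair of visits all have the same variance. With visits at 0, 1 and 3 months, a correlation that fades with time breaks this, because the 3-month change then varies more than the 1-month change. Follow-up contrasts that borrow the pooled within-patient error are hit harder than the overall F test, and the change from baseline to 3 months is the contrast a reader will look for.

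**Working it through.** **The plan's own figure.** The 4 per group cannot be reproduced, because no alpha, power, effect size or SD is stated. The check below takes 4 v 4 as given and assumes two-sided 5%.

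**1. Observed 3-month values that are discarded.** Let q be the chance that any one follow-up value is missing, independently across visits, with baseline complete. The documents give no rate; q = 0.05 to 0.10 is assumed.

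- Month 1 missing and month 3 observed, per patient: q(1−q) = 0.0475 or 0.09.
- At least one such patient among 8: 1−(1−q(1−q))^8 = 1−0.9525^8 = 0.32, or 1−0.91^8 = 0.53.
- At least one patient incomplete for either reason: 1−(1−q)^16 = 0.56 or 0.81.
- Share of incomplete patients whose 3-month value exists: q(1−q)/(1−(1−q)^2) = 0.49 or 0.47.

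**2. What losing a patient costs.** The 95% CI half-width for the group difference in 3-month change, in SDs of that change, is t(0.975, df) × √(1/a + 1/b).

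| Patients | Contrast's own variance | Pooled error, if sphericity holds |
|---|---|---|
| 4 v 4 | 1.73 (6 df) | 1.54 (12 df) |
| 3 v 4 | 1.96 (5 df), +13% | 1.70 (10 df), +10% |
| 3 v 3 | 2.27 (4 df), +31% | 1.88 (8 df), +22% |

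The planned ANOVA corresponds to the right-hand column.

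**3. Sphericity.** Simulated type I error of the group-by-time test, 4 v 4, visits at 0, 1 and 3 months, nominal 5%, at least 100,000 runs per scenario. All covariances are assumed.

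| Scenario | Uncorrected F(2,12) | Greenhouse-Geisser |
|---|---|---|
| Compound symmetry, correlation 0.6 | 5.0% | 3.6% |
| Correlation decaying 0.6 per month | 5.7% | 4.1% |
| Decaying 0.8 per month | 6.2% | 4.4% |
| Decaying 0.9 per month | 6.2% | 4.4% |
| Decaying 0.7, SD 1, 1.3, 1.8 | 6.6% | 4.6% |
| Strong random slopes | 8.5% | 5.1% |

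Two further cases with growing SD gave 6.9% (decay 0.9; SD 1, 1.2, 1.5) and 8.1% (correlations 0.9, 0.5, 0.5; SD 1, 1.1, 1.6) for the uncorrected test.

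**4. The 3-month contrast.** Take a correlation decaying by 0.8 per month and SD 1. The variances of the differences are 2(1−0.8) = 0.400 (0 to 1 month), 2(1−0.64) = 0.720 (1 to 3) and 2(1−0.512) = 0.976 (0 to 3). Pooled error uses their mean, (0.400 + 0.720 + 0.976)/3 = 0.699, for a contrast whose variance is 0.976, which is 28% too small. By simulation, with decay of 0.7 to 0.9 per month and with growing SD, the pooled-error contrast rejects about 9% to 11% of the time at nominal 5%, before any Tukey adjustment. The same contrast with its own variance on 6 df rejects 4.9% to 5.1%.

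**5. What a mixed model does and does not repair.** On one complete data set, a random-intercept REML model with group, visit and group-by-visit gave the same interaction F as the ANOVA (0.16945 in both), so its sphericity error is the same. An unstructured covariance with a small-sample F test held 5.0% in every scenario. With a large-sample Wald chi-square it gave about 18%. The unstructured test costs power: 53% v 70% for the ANOVA under compound symmetry, with a difference of 2 SD at month 3 and half that at month 1.

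**The case against.** The strongest reply is that this is a 4 v 4 pilot, with feasibility as a stated purpose and no alpha given, so one extra percentage point of type I error changes little. Greenhouse-Geisser repairs the overall test without changing the model, and the unstructured model starts out 12% wider than the ANOVA if sphericity holds (1.73/1.54 = 1.12). Most of this stands. It is why a named correction within the ANOVA is acceptable, and why the cost of the alternative must be stated. It does not dispose of the discarded values or of the pooled-error contrasts, which Greenhouse-Geisser leaves untouched.

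It is also fair that dropping incomplete patients is a convention of the method and not a rule in Section 8.0. No software is named, and some programs fit such layouts by likelihood. The visit windows give some protection against missed visits, though none against a failed recording.

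Four stronger readings may tempt a reader, and the documents do not support them:

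- *Any mixed model with the same terms removes both problems.* A random-intercept or compound-symmetry model solves only the missing-value problem.
- *The 56% to 81% chance of an incomplete patient measures the avoidable loss.* About half of those patients lack the 3-month value itself, and no model restores it.
- *The +13% and +31% half-widths are the planned ANOVA's loss.* They belong to a t comparison of change; the pooled-error figures are +10% and +22%.
- *Uneven spacing by itself violates sphericity.* It does so only if correlation or SD changes with time, which is plausible but assumed here.

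**Conclusion.** The point holds and is worth a small change. As conventionally run, the named analysis can throw away observed 3-month data, with a 32% to 53% chance of affecting at least one patient on a given outcome if 5% to 10% of follow-up values are missing. Its uncorrected time and group-by-time tests are mildly anti-conservative under plausible covariances: about 6%, or about 7% to 8% if the SD grows. The pooled-error contrast of 3-month change is worse, at about 9% to 11% before Tukey. The between-group main effect is not affected by sphericity.

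The missing rates, their independence across visits, the correlations and the SDs are all assumptions; the documents supply none. Whether to insist on an unstructured covariance with 8 patients is debatable. Using every observed value, and not relying on uncorrected pooled-error tests, is not.

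**What to change.** In Section 8.0, state that all observed visits are analysed with a REML linear mixed model with fixed effects for group, visit and group-by-visit and Kenward-Roger degrees of freedom. Name the covariance structure and any fallback in advance, and say that a random-intercept or compound-symmetry structure, including as a fallback, still assumes sphericity. Report the 3-month group difference in change with that contrast's own variance (6 df with complete data) and a 95% CI; for a pilot, this estimate matters more than the overall test. If the ANOVA is kept, report Greenhouse-Geisser P values and state how a patient with a missing visit is handled.

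The cost is two or three sentences and standard software, with no change to visits, treatment or sample size. The downsides should be written down too:

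- Unstructured covariance means six parameters per outcome in 8 patients and may not converge.
- It loses precision if sphericity holds (half-width 1.73 v 1.54 SD; power 53% v 70% in the case shown).
- Greenhouse-Geisser is slightly conservative in that same case (3.6%).
- The mixed model relies on data being missing at random.
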